10.3 Data Analyses Plans

Summary of Analytic plan for primary objective	Summary of Analytic plan for secondary objectives

Please refer to the below sample size justification for the parallel Simon's two stage design which defines how the endpoints are met.
 
For Group A. Estimated ORR for historical control is 20% versus target ORR of 40% for nivolumab and metformin combination treatment.
	
Depth of response: waterfall plot Duration and persistence of response: swimmer's plot PFS: PFS at 1 and 2 years (Kaplan-Meier analysis) OS: OS at 1 and 2 years (Kaplan-Meier analysis) ORR, DCR by irRC (descriptive statistics,

NU Study Number: NU 16L04
Other Study Number: CA 209-801

For Group B. Estimated ORR for refractory patients is 5% versus target ORR of 40% for niovulomab and metformin combination treatment.
	
exact binomial confidence intervals) We will use descriptive statistics and graphical displays to evaluate change in serum biomarkers between pre- and post-treatment. A Wilcoxon signed rank test will be used to determine if there is a statistically significant change in serum biomarkers. Toxicities will be tabulated by type and grade.

--	---

The primary analysis will be on the evaluable analysis set, including all evaluable patients regardless of drug exposure. Clinical benefit rate will be defined as stable disease (for ≥ 12 weeks), complete or partial response by both the Response Evaluation Criteria in Solid Tumors (RECIST) and irRECIST. Maximum response prior to disease progression will be used. The overall response rate will be estimated by the proportion of overall response, and its 80% confidence interval (CI) and 95% CI will be estimated using the exact binomial distribution.

Additionally, we will evaluate overall response rate, defined as complete or partial response using RECIST guidelines in a similar manner. We will also perform similar analyses using Immune Related RECIST (irRECIST). Duration of response, defined as the duration from the first documentation of clinical benefit to the first documented progressive disease or death of any cause, whichever occurs first, will also be analyzed. For patients alive and progression-free at the time of data cut off, duration of response will be censored as of the last tumor assessment date. Duration of response will only be evaluated for the subgroup of patients with a clinical benefit using the Kaplan-Meier method.

PFS is defined as the time from treatment initiation to documented disease progression. OS is defined as the time from the start of treatment until death due to any cause. For patients alive at the time of data cut-off, PFS and OS will be censored as of the last tumor assessment date or known to be alive, respectively. The PFS and OS will be estimated using the Kaplan-Meier method. The number, frequency, and severity of adverse events (as defined by the NCI Common Terminology Criteria for Adverse Events or CTCAE version 4.03) will be recorded.

Baseline percent PDL1 expression, TILs (sTILs, iTILs, and their ratio), and changes in T cell subpopulations will be used as a continuous variable to predict clinical benefit or overall response rates using appropriate statistical summaries. Cox proportional hazards regression will be used to compare how these biomarkers are associated with PFS and OS as well.

Changes in these biomarkers will also be analyzed to assess for pharmacodynamic effects of treatment. Continuous variables will be analyzed using either paired t-tests (normally distributed data), signed rank tests (non-normally distributed data) or repeated measures analysis of variance (correlated normally distributed data).

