Group A and Group B will address two clinical questions. Group A is designed to assess possible synergistic effect of the combination treatment in immunotherapy naïve patients whereas group B is designed to determine whether the combination treatment of metformin with immunotherapy can overcome resistance to single agent PD-1/PD-L1 inhibitors.

Group A: In order to demonstrate synergy in anti-tumor effect, ORR of the combination treatment will be compared to that of historical control (20%) reported in phase 3 single agent nivolumab trials in lung cancer (CheckMate057 and CheckMate017). Optimal Simon's two stage design will be used with target ORR of 40% versus control ORR of 20% (type 1 error rate of 0.1 and power of 0.8)

Group B: In order to find signal in patients with prior exposure to single agent PD-1/PD-L1 inhibitors, ORR of the combination treatment will be described. Optimal Simon's two stage design will be used with target ORR of 20% versus control ORR of 5% (type 1 error rate of 0.1 and power of 0.8).

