10.2 Sample Size and Accrual

Up to 49 patients (Arm A=24, Arm B=25) will be entered into the trial based on optimal Simon two stage design as below.

Arm A: In the first stage, 9 patients will be entered. If no patients show a response, then the trial will be terminated due to inactivity of the treatment. If 1 or more of 9 show a response, then an additional 15 patients will be added. If 2 or fewer of 24 show a response, then the trial will conclude that the response rate could be as low as 5%. If 3 or more respond, then the trial will conclude that the response rate is at least 20%. This design has a 20% chance of falsely concluding the rate is 5% (false negative Type II error rate = 20%, or power = 80%), and a 10% chance of falsely concluding that the rate is 20% (false positive Type I error rate = 10%). There is a 63% probability of early termination of the trial when the true response rate is 5%.

Arm B: In the first stage, 12 patients will be entered. If 2 or less patients show a response, then the trial will be terminated due to inactivity of the treatment. If 3 or more of 12 show a response, then an additional 13 patients will be added. If 7 or fewer of 25 show a response, then the trial will conclude that the response rate could be as low as 20%. If 8 or more respond, then the trial will conclude that the response rate is at least 40%. This design has a 20% chance of falsely concluding the rate is 20% (false negative Type II error rate = 20%, or power = 80%), and a 10% chance of falsely concluding that the rate is 40% (false positive Type I error rate = 10%). There is a 56% probability of early termination of the trial when the true response rate is 5%.

Due to inevaluable patients and dropout, target accrual will be 51 patients. It is anticipated that 2 patients will be accrued per month so that accrual to this study will take 2 years.

Thus, this study will be a single institution trial with duration of enrollment being 2 years. The study will be done via both internal and external referral system. Being one of the busiest lung cancer programs in the area with good advertisement plan towards partnering institutions on this clinical trial, the above accrual plan is deemed to be a feasible one.

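### Group B's response-rate hypotheses are stated three ways, and the 5% versus 40% pair in the 10.3 analysis table matches no design printed in the plan

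*Combined protocol and SAP*

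**What the plan says.** The plan uses Group and Arm for the same split. A is naive to PD-1/PD-L1 inhibitors and B has been treated with them (sections 1.3.2 and 3.1.3).

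The hypotheses for B appear in three forms:

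- **Section 1.3.2:** an optimal Simon two-stage design with "target ORR of 20% versus control ORR of 5% (type 1 error rate of 0.1 and power of 0.8").
- **Section 10.3, table, plan for the primary objective:** "Estimated ORR for refractory patients is 5% versus target ORR of 40" percent. The same cell sends the reader to the sample size justification for how the endpoints are met.
- **Section 10.2 and the Study Summary, under Arm B:** a null of 20% against 40%, with 12 patients in stage 1. On stopping, 10.2 says "If 2 or less patients show a response, then the trial will be terminated due to inactivity of the treatment"; on continuing, "If 3 or more of 12 show a response, then an additional 13 patients will be added". Eight or more responses among 25 count as success. Power is given as 80% and type I error as 10%.

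The hypotheses for A agree between 1.3.2 ("Optimal Simon's two stage design will be used with target ORR of 40% versus control ORR of 20" percent) and 10.3 ("Estimated ORR for historical control is 20% versus target ORR of 40" percent). Section 10.2 and the Study Summary, however, print a 5% versus 20% design under Arm A: 9 patients, then 24, with success at 3 or more. On size, 10.2 states: "Up to 49 patients (Arm A=24, Arm B=25) will be entered into the trial".

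**The concern.** The null and target rates decide which stopping boundary and sample size belong to an arm, and what its result may be said to show. The table headed as the analytic plan for the primary objective gives Group B a pair that appears nowhere else. Its null agrees with 1.3.2 and its target agrees with 10.2, but the pair agrees with neither.

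Someone preparing the final analysis therefore cannot tell from the text whether success in Group B means ruling out 5% or ruling out 20%, or which improvement the arm was sized to detect.

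**Working it through.** **Inputs.** Rates from 1.3.2, 10.2 and 10.3 as listed above. Type I error 0.10 and power 0.80 from 1.3.2 and 10.2. The two printed rules from 10.2, written r1/n1, r/n: stop if r1 or fewer of n1 respond; declare success if more than r of n respond.

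**Formulas.** With X ~ Bin(n1, p) and Y ~ Bin(n − n1, p):

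- probability of early termination: PET(p) = P(X ≤ r1)
- P(success | p) = Σ over x from r1+1 to n1 of P(X = x) · P(Y > r − x)
- expected size: EN = n1 + (1 − PET)(n − n1)

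The optimal design has the smallest EN under the null among those with type I error ≤ 0.10 and power ≥ 0.80.

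**Step 1: reproduce the plan's own figures.**

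| Rule | True rate | P(success) | PET |
|---|---|---|---|
| 2/12, 7/25 (printed under Arm B) | 5% | below 0.0001 | 0.980 |
| | 20% | 0.099 | 0.558 |
| | 40% | 0.815 | 0.083 |
| 0/9, 2/24 (printed under Arm A) | 5% | 0.093 | 0.630 |
| | 20% | 0.805 | 0.134 |
| | 40% | 0.990 | 0.010 |

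Both printed rules are sound for the rates printed beside them. 2/12, 7/25 has type I error 0.099 at 20% and power 0.815 at 40%. 0/9, 2/24 has type I error 0.093 at 5% and power 0.805 at 20%. The 56% early-termination figure given for Arm B reproduces at a true rate of 20% (0.558), not at the 5% stated beside it (0.980).

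**Step 2: find the optimal design for each stated pair.** The search covered every design with n up to 32 for the first two pairs and up to 28 for the third.

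| Null v target | Where stated for B | Optimal design | Type I error | Power | EN under null |
|---|---|---|---|---|---|
| 5% v 20% | 1.3.2 | 0/9, 2/24 | 0.093 | 0.805 | 14.55 |
| 20% v 40% | 10.2, Study Summary | 2/12, 7/25 | 0.099 | 0.815 | 17.74 |
| 5% v 40% | 10.3 | 0/4, 1/8 | 0.046 | 0.826 | 4.74 |

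The last row can be checked by hand, since success needs at least 1 response in the first 4 patients and at least 2 in all 8:

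- At 5%: P(X=0) = 0.95⁴ = 0.8145, P(X=1) = 4 × 0.05 × 0.95³ = 0.1715, P(X≥2) = 0.0140. P(success) = 0.1715 × (1 − 0.8145) + 0.0140 = 0.046.
- At 40%: P(X=0) = 0.6⁴ = 0.1296, P(X=1) = 4 × 0.4 × 0.6³ = 0.3456, P(X≥2) = 0.5248. P(success) = 0.3456 × 0.8704 + 0.5248 = 0.826.

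Even with type I error at 0.05 and power at 0.90, the optimal 5% versus 40% design stops at 14 patients (0/5, 2/14).

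**Step 3: compare.** The 5% versus 40% pair calls for 8 patients, about a third of the 24 or 25 planned per arm (8/24 = 0.33; 8/25 = 0.32). The other two pairs reproduce the two printed designs exactly. Relative to 1.3.2, those designs stand under the opposite arms.

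**The case against.** Three points can be made on the other side.

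**The 40% target is not isolated.** Section 10.2 and the Study Summary also attach 40% to Arm B, so on the target alone 1.3.2 is the outlier and 10.3 differs from 10.2 only in its null. This stands. A reader might infer from the sample size that only a 20% target can have been meant. The documents do not support that without a condition: 25 patients is exactly the optimal size for 20% versus 40%. The inference needs the null fixed at 5%, as 1.3.2 and 10.3 both have it, and even then the matching size is 24, printed under Arm A.

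**The figure in 10.3 drives no decision.** The table defers to the sample size justification, and no printed boundary, size or error rate is calculated from 5% versus 40%. This stands too. A reader might infer that the 40% in 10.3 causes, or conceals, the roughly 10% power of the Arm B rule at a 20% response rate. It does not cause it: the rule in 10.2 is the same whatever 10.3 prints. That anyone would be misled is conjecture, since 10.2 states the 20% null beside its rule.

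**It may be only a slip carried over from Group A.** That is plausible, but the documents do not say so. It would explain the contradiction without removing it. Nor is this superseded text, because the summary of changes does not touch either figure.

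**Conclusion.** The contradiction is real. Group B has three hypothesis pairs in current text, and the one in the primary-analysis table corresponds to no printed design. At the plan's error rates and a 5% null, a 40% target needs at most 8 patients under the optimal design, against 24 for a 20% target.

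Taking 5% versus 20% as the intended pair is an inference, though a well-supported one. Section 1.3.2 ties the 20% control rate to single-agent nivolumab trials and assigns it to the naive group. Sections 1.3.2 and 10.3 agree on Group A's pair and on Group B's 5% null.

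If 1.3.2 governs, the rule printed under Arm B has power 0.099 at Group B's target and stops after 12 patients with probability 0.558. That shortfall belongs to the apparent interchange of the two rules in 10.2 and the Study Summary. The 40% in 10.3 is a separate error: swapping the rules would still leave a target there that fits no Group B design.

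**What to change.** 1. In the 10.3 table, change Group B to a 5% null and a 20% target, as in 1.3.2.
2. In the same edit, reconcile the Arm A and Arm B paragraphs in 10.2 and the Study Summary with 1.3.2, so that Group B carries 0/9, 2/24 (type I error 0.093, power 0.805) and Group A carries 2/12, 7/25 (type I error 0.099, power 0.815). Doing step 1 alone would leave Arm B with power 0.099 at its newly stated target.
3. Where the 56% early-termination probability is given, attach it to a true rate of 20%.
4. If 40% is really intended for Group B, correct 1.3.2 instead, and restate Group B's null, size and power for that target.

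The cost is one figure in 10.3 plus the arm labels and per-arm sizes in 10.2 and the Study Summary. The totals do not move: 25 + 24 = 49 evaluable at the maximum, 12 + 9 = 21 at the minimum, and the accrual target stays at 51. If stage 1 boundaries have already been applied to either arm, record which rule was used.

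### The fixed-sample exact CIs planned for ORR ignore the two-stage design, so at the smallest passing result of each design (3/24, 8/25) the 80% CI contains the null just rejected

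*Combined protocol and SAP*

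**What the plan says.** Section 10.2 states that patients "will be entered into the trial based on optimal Simon two stage design as below". It sets two designs, each with Type I error 10% and power 80%.

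- **9/24 design, null 5%, target 20%.** "In the first stage, 9 patients will be entered. If no patients show a response", the arm stops. At the end, "If 2 or fewer of 24 show a response, then the trial will conclude that the response rate could be as low as 5"%, and "If 3 or more respond, then the trial will conclude that the response rate is at least 20"%.
- **12/25 design, null 20%, target 40%.** "In the first stage, 12 patients will be entered. If 2 or less patients show a response", the arm stops. At the end, "If 8 or more respond, then the trial will conclude that the response rate is at least 40"%.

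Section 10.3 refers to the two-stage design as what defines how the endpoints are met. For the point estimate it says: "The overall response rate will be estimated by the proportion of overall response". For the interval, the same sentence goes on to say that "its 80% confidence interval (CI) and 95% CI will be estimated using the exact binomial distribution". A later paragraph of 10.3 treats complete or partial response by RECIST in a similar manner, so the method reaches the primary ORR. Neither the Study Summary nor Section 10 adjusts the interval for the interim stop.

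**The concern.** A two-sided 80% interval leaves 10% in each tail, so it is the interval that corresponds to a one-sided 10% test. A reader will expect its lower limit to lie above the null when the arm passes. An ordinary exact binomial interval assumes that 24 or 25 patients were always going to be treated. It therefore counts paths to a high total that the stage 1 stop rules out, and it is calibrated to a different test from the one the trial runs. What is at stake is the report of the primary result: a pass at the 10% level could be printed beside an 80% CI that includes the rejected null. If the interval is not fixed in advance, the method might be chosen after the data are seen.

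**Working it through.** **Inputs.** From 10.2: (r1/n1, r/n) = (0/9, 2/24) with rates 5% and 20%, and (2/12, 7/25) with rates 20% and 40%. From 10.3: exact binomial, 80% and 95%. No variant is named, so I take Clopper-Pearson.

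**1. Reproduce the plan's figures.** With X1 the stage 1 responses and X2 the stage 2 responses, P(stop) = P(X1 ≤ r1), and P(pass) = Σ over x1 > r1 of P(X1 = x1) · P(X2 ≥ r + 1 − x1).

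| Design | P(stop) at null | P(pass) at null | P(pass) at target |
|---|---|---|---|
| 9/24 | 0.630 | 0.0931 | 0.805 |
| 12/25 | 0.558 | 0.0991 | 0.815 |

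These agree with the stated 63%, 56%, 10% and 80%. (The 56% holds at a true rate of 20%; 10.2 prints it as holding at 5%, where it would be 98%.)

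**2. Planned 80% CI at the smallest pass.** Lower limit = 0.10 quantile of Beta(x, n − x + 1); upper limit = 0.90 quantile of Beta(x + 1, n − x).

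- 3/24 = 12.5%: 4.68% to 25.8%. Contains 5%.
- 8/25 = 32.0%: 19.62% to 46.7%. Contains 20%.

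**3. Why they disagree with the rule.** The fixed-sample tail at the null is P(X ≥ 3 | 24, 5%) = 0.1159 and P(X ≥ 8 | 25, 20%) = 0.1091, both above 0.10. The design's tails are 0.0931 and 0.0991. The differences, 0.1159 − 0.0931 = 0.0228 and 0.1091 − 0.0991 = 0.0100, are the paths that the stage 1 stop removes. For the 9/24 design this is P(X1 = 0) · P(X2 ≥ 3 of 15) = 0.630 × 0.0362 = 0.0228.

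**4. Two-stage interval.** Rank early stops below all stage 2 outcomes. The lower limit solves P(continue and X ≥ x) = 0.10. The upper limit solves P(stop) + P(continue and X ≤ x) = 0.10.

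| Result | Planned 80% CI | Two-stage 80% CI | Null |
|---|---|---|---|
| 3/24 | 4.68% to 25.8% | 5.16% to 27.9% | 5% |
| 8/25 | 19.62% to 46.7% | 20.04% to 47.4% | 20% |

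For an arm stopped at stage 1, this ordering gives the ordinary interval on n1, so nothing changes there.

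**5. How far the conflict reaches.** One more response removes it: the planned lower limit is 7.5% at 4/24 and 23.0% at 9/25. The boundary result makes up 72% (0.067/0.093) and 55% (0.055/0.099) of passes under the null, and occurs in 11.6% and 10.5% of trials at the target rate.

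**6. Coverage of the planned interval under two-stage sampling** (enumerated over true rates up to 70%, early stops using n1).

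| Design | Worst upper miss, 80% CI (nominal 10%) | Lowest 80% coverage | Worst upper miss, 95% CI (nominal 2.5%) |
|---|---|---|---|
| 9/24 | 13.8% | 78.9% | 3.8% |
| 12/25 | 15.0% | 79.2% | 3.9% |

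The excess is in one direction: the upper limit is too low.

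**The case against.** The strongest reply is that the interval decides nothing. Section 10.3 leaves success to the two-stage rule and never uses a CI as a test, so pairing the 80% CI with the 10% rule is an inference from the matching tail areas. That stands, and it rules out the stronger reading that the decision or its error rates are wrong: step 1 shows that they are met.

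The conflict is also narrow. It arises at one result per design, the lower limits miss the null by 0.3 and 0.4 points, and overall coverage is close to nominal. At 8/25 the corrected limit of 20.04% prints as 20.0% to one decimal. A mid-p interval would exclude both nulls (lower limits 5.7% and 21.1%), though that is not what exact binomial usually means. All of this limits the size of the point without removing it.

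A reader might also infer that the reported ORR is biased low and should be replaced by the unbiased estimator (UMVUE) for two-stage designs. This is not supported. The downward bias of the raw proportion (−2.0 points at 5% and −1.7 at 20% for 9/24; −2.5 at 20% and −1.1 at 40% for 12/25) averages in the trials stopped early. Among trials that reach stage 2, where the conflict arises, the raw proportion is biased high: +3.2 and +1.2 points, and +5.1 and +1.1. There the UMVUE is further off (+8.5 and +3.1; +10.7 and +2.3), and it would show a failing 3/25 as 25.0%, above the 20% null. The simple proportion in 10.3 is a defensible choice.

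Finally, the 95% CI contains the null at 3/24 and 8/25 under either method (two-stage: 2.9% to 36.1%; 15.3% to 54.5%). That follows from its higher confidence level and is no fault.

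**Conclusion.** The concern holds for the interval only. As written, 10.3 prescribes an 80% CI that contradicts the trial's own test at the smallest passing result of each design, and whose upper limit errs low more often than its nominal 10%. It is a reporting inconsistency worth correcting; it does not threaten the go/no-go decision.

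The finding assumes that exact binomial means Clopper-Pearson and that the stages are run at the planned sizes. It attaches to each design with its own null rather than to a labelled arm. Section 10.2 gives Arm A the 5% null and Arm B the 20% null, while 1.3.2 and the table in 10.3 pair them the other way round. The result is the same whichever pairing is adopted, provided each design keeps its null.

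**What to change.** In 10.3, keep the raw proportion as the ORR estimate and replace the interval wording with text such as:

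*For each arm, 80% and 95% exact confidence intervals for the primary ORR will be obtained by inverting the sampling distribution of the two-stage design under stage-wise ordering, with early stops ranked below all stage 2 outcomes. Lower limits will be reported to two decimals.*

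Two decimals are needed so that 20.04% is not printed as 20.0%. The cost is a few lines of code and a slightly less familiar interval. After stage 2 both limits move up, the upper one more (at 3/24, from 25.8% to 27.9%), so the interval is somewhat wider. Patients, sample size and decision rule are unaffected.

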8. The same modality used at baseline should be used throughout for imaging. CT imaging with contrast will occur every 2 cycles starting with Cycle 3 Day 1 (\pm 7 days) and should include chest, abdomen, and pelvis. Neck will be included only if measurable lesions are present. Metformin should be held prior to scans per each institutional protocol. Tumor measurements will be performed using RECIST 1.1. Progressive Disease (PD) must be confirmed by repeat scan within 8 weeks at least after 4 weeks. Patients with a known history of CNS disease must have CNS imaging at screening to rule out activity.
9. Patients will undergo a fresh tissue biopsy prior to study enrollment, unless deemed to be clinically inappropriate per PI. If not feasible, archived tissue will be used (if available).
10. The maximum time interval between registration and the first dose of study drug will be 14 days
11. Nivolumab will be given as follows:
Cycle 1-4: 240mg IV over 30 minutes (-5 / +15 minutes) every 14 days (Day 1 & 15, \pm 3 days)
Cycle 5+: 480mg IV over 60 minutes (-10 / +15 minutes) every 28 days (Day 1, \pm 3 days) until disease progression, intolerance, or withdrawal of consent.
12. Metformin will be dispensed Day 1 of each cycle. Dosing will begin at 1,000mg po once daily and escalate by 500mg every 7 days until the final dose of 2,000mg is reached. Patients will return unused drug and drug bottles at each study visit and will maintain a drug diary to track compliance.
13. The end of treatment visit should occur 30 days after the last dose of study treatment (+/- 7 days) or before starting another line of treatment, whichever comes first.
14. Correlatives from peripheral blood will be collected for all patients at Induction Day 1, C1D1, C3D1, and at the EOT. Biopsy samples (fresh or archived) will be collected for all patients if possible. See separate lab manual for specifications. See section 9.0 for details.
15. Metformin monotherapy will be given at 1,000mg PO QD during the 7-day Induction period, prior to starting nivolumab on Cycle 1 Day 1.
16. After patients come off treatment they will be followed up at 3, 6, 9, and 12 months (\pm 7 days) and then every 6 months (\pm 14 days) for 3 years for survival and progression of disease via either clinic visits or phone calls.

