6.2 Immune-related RECIST (irRECIST)

- 6.2.1 In addition to above, tumor response will be assessed by the irRECIST for investigational purposes, not assessment of primary objective or treatment decisions.¹³ In RECIST v1.1, the appearance of new lesions indicates PD. However, in irRECIST, new measurable lesions are incorporated in the tumor burden, which is used to determine irPD, immune-related partial response (irPR), and immune-related complete response (irCR). New nonmeasurable lesions preclude irCR. Under RECIST v1.1, there is no confirmation for PD. Under irRECIST, responses and irPDs must be confirmed by consecutive scans at least 4 weeks apart, assuming no clinical deterioration. We will define immune-related clinical benefit rate as immune-related stable disease (irSD), irPR, or irCR.

NU Study Number: NU 16L04
Other Study Number: CA 209-801

Table 6-1: Immune-related Response Evaluation Criteria: Overall Response

Tumor Burden (Baseline and New)	Non-Target Lesions (Baseline and New)	Response
Disappearance of non-nodal lesions. All pathologic lymph nodes <10 mm (short axis)	Disappearance of non-nodal lesions. All pathologic lymph nodes < 10 mm (short axis)	irCR
≥30% decrease from baseline	Any	irPR
≥20% increase from nadir and at least 5 mm	Any	irPD
Neither sufficient decrease to qualify for PR, nor sufficient increase to qualify for PD	Any	irSD
Disappearance of all non-nodal lesions. All pathologic lymph nodes <10 mm	Any other than disappearance of all non-nodal lesions and reduction of pathologic lymph nodes <10 mm	irPR
Not all evaluated	Any	irNE

irCR = immune-related complete response; irPD = immune-related progressive disease; irPR = immune-related partial response; irNE = immune-related not evaluable; irSD = immune-related stable disease;

-Tumor burden is the sum of single diameters (short axis for nodal lesions, longest diameter for other lesions) for the target lesions. In subsequent scans, the diameters of new measurable lesions are added to the tumor burden.

-Best overall response based on 2 consecutive measurements at least 4 weeks apart.

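### Section 10.3 gives no PFS status to a patient who dies without documented progression, and its duration of response includes patients who never responded

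*Combined protocol and SAP*

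**What the plan says.** **PFS.** Section 10.3 states that "PFS is defined as the time from treatment initiation to documented disease progression". The sentence after it defines OS by death from any cause. The censoring rule follows: "For patients alive at the time of data cut-off, PFS and OS will be censored as of the last tumor assessment date" (for OS, the date last known alive). PFS is to be reported at 1 and 2 years by Kaplan-Meier, and "Cox proportional hazards regression will be used to compare how these biomarkers are associated with PFS and OS as well". The other sections that mention PFS (Study Summary, 2.2, 6.4, 10.1) name it without defining it. Section 4.7 refers only to the time of progression.

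**Duration of response.** Section 10.3 has it "defined as the duration from the first documentation of clinical benefit to the first documented progressive disease or death of any cause", and adds: "Duration of response will only be evaluated for the subgroup of patients with a clinical benefit using the Kaplan-Meier method". Clinical benefit is defined there too: "Clinical benefit rate will be defined as stable disease (for ≥ 12 weeks), complete or partial response", under both RECIST and irRECIST. Section 6.1.7 counts only complete and partial responses as objective response. Section 6.2 says: "We will define immune-related clinical benefit rate as immune-related stable disease (irSD), irPR, or irCR", with no minimum duration.

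**Scans.** Section 5.0, footnote 8: "CT imaging with contrast will occur every 2 cycles starting with Cycle 3 Day 1", with a window of 7 days either way. The same footnote asks for progression to be confirmed by a repeat scan 4 to 8 weeks later. Footnote 15 places a 7-day metformin induction before Cycle 1 Day 1.

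**The concern.** Read literally, a death without documented progression is not a PFS event, and the censoring rule does not reach it because the patient is not alive at cut-off. Two analysts could count, drop or censor the same death and report different 1- and 2-year PFS from the same data. The biomarker Cox models on PFS would inherit that choice. The censoring sentence also says alive rather than alive and progression-free, whereas the duration-of-response sentence has the fuller wording.

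The quantity called duration of response is the only planned summary estimate under that name, and it includes patients whose best outcome was stable disease. Someone reading the result would take it to describe responders.

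**Working it through.** The plan states no PFS rate, event count or duration target, so there is no figure to reproduce. The check is of the text, with illustrations of size.

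**1. Status of each patient under the PFS text**

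- Progression documented: event.
- Alive at cut-off: censored at the last tumour assessment. Taken literally, this also covers a living patient who has already progressed.
- Dead without documented progression: no rule.

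Duration of response, in the same section, ends at progression or death and censors patients who are alive and progression-free.

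**2. How many deaths could precede the first scan**

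Two 28-day cycles put Cycle 3 Day 1 at week 8 from Cycle 1 Day 1. Inputs from section 1.4.2 are 42% 1-year survival on nivolumab (second-line squamous phase 3 study) and a median OS of 9.9 months (heavily pretreated NSCLC). A constant hazard is assumed.

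- 42% at 1 year: 1 − 0.42^(8/52) = 0.125; × 24 = 3.0 patients.
- Scan at week 7, the early edge of the window: 1 − 0.42^(7/52) = 0.110; × 24 = 2.6.
- Counted from induction day 1 (9 weeks): 1 − 0.42^(9/52) = 0.139; × 24 = 3.3.
- Median 9.9 months = 43.05 weeks: 1 − 0.5^(8/43.05) = 0.121; × 24 = 2.9.

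These counts assume that none of the deaths had progression documented clinically. Neither input describes a PD-1-refractory population, so Arm B has no comparable anchor.

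**3. Effect on 1-year PFS, with true PFS S assumed**

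If the deaths in step 2 are the only events before the first scan, dropping or censoring them gives S/(1 − 0.125):

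| Assumed S | Reads as |
|---|---|
| 10% | 11.4% |
| 20% | 22.9% |
| 30% | 34.3% |

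If half of them had progression documented clinically, 20% reads 0.20/(1 − 0.0625) = 21.3%.

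Timing matters. Suppose instead that such deaths are a constant share f of first events throughout. With complete follow-up, dropping them returns S on fewer patients. Censoring them gives S^(1−f): at S = 20%, 23.5%, 27.6% and 32.4% for f = 10%, 20% and 30%. If deaths count as events, the estimate is S in every case.

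For scale, the approximate 95% half-width at S = 20% and n = 24 is 1.96 × √(0.2 × 0.8/24) = 0.160. The 7-day choice of origin is worth 0.20^(358/365) − 0.20 = 0.006.

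**4. Start date for duration of response**

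Scans fall at about weeks 8, 16 and 24, with none at week 12.

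- Stable disease at weeks 8 and 16, progression at week 24: the duration is 24 − 8 = 16 weeks or 24 − 16 = 8 weeks, depending on which scan first documents benefit.
- Stable disease at weeks 8 and 16, PR at week 24: the clock may start at week 8, 16 or 24.

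**5. Effect of pooling (illustration)**

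Assume an ORR of 20% and stable disease of at least 12 weeks in 20 to 40%. Never-responders are then 0.20/0.40 = 50% to 0.40/0.60 = 67% of the set. Take the 17-month responder median from section 1.4.2 and assume a stable-disease median of 4 to 8 months. The pooled median t solves w·2^(−t/m) + (1 − w)·2^(−t/17) = 0.5, where w is the never-responder share and m the stable-disease median in months. With w = 0.50 and m = 8, t = 11.4 months; with w = 0.67 and m = 4, t = 5.9 months.

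**The case against.** The strongest reply is that context settles the PFS reading. The endpoint's name includes survival, the preceding paragraph of 10.3 counts death for duration of response, and limiting censoring to living patients leaves a death nowhere to go except among the events. The word alive is evident shorthand, since nobody intends to censor a living patient who has progressed. This is persuasive about intent, and it is why the gap is best called a drafting omission. It does not supply the missing rule.

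The figure of 3 of 24 is close to an upper bound. Section 6.1.2 bases tumour assessment on physical examination as well as radiology, so progression can be documented before Cycle 3 Day 1. That stands.

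On duration of response, the plan does state a start event, an end, censoring and a population, and including stable disease is an explicit choice. The natural start for a stable-disease patient is arguably the first scan at or beyond 12 weeks. The planned swimmer's plot can show responders individually. That makes this part mainly a matter of label and start date, but the plot gives no responder estimate and the date is still unwritten.

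Three stronger readings are tempting and unsupported. A reader might infer that the trial will overstate 1-year PFS by the 3.5 to 12.4 points that censoring gives in step 3; section 10.3 does not authorise censoring a death, and the shares are assumed. A reader might infer from section 4.8 that progression follow-up stops at subsequent therapy and that an extra sensitivity analysis is needed; the sentence that follows there has all subjects followed for survival and progression. A reader might also infer a harmful comparison with the 17-month figure; no such comparison is planned, and section 1.3.2 sets only ORR against a historical control.

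**Conclusion.** The point holds on the text. As written, section 10.3 assigns no PFS status to a death without documented progression and does not limit censoring to progression-free patients, and no other section repairs either. The size cannot be derived from the documents: it is zero if such deaths are counted as events. In the early-death illustration at an assumed 20% it is about 3 points upward, well inside the 16-point half-width. That illustration rests on a constant hazard, on 42% survival carried over from another population, and on no clinically documented progression.

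Duration of response, as defined, includes never-responders. Its start date is unclear both for stable-disease patients and for those with stable disease before a later response. Under irRECIST, membership of the set is also unclear because 6.2 and 10.3 define clinical benefit differently.

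The affected results are secondary single-arm estimates and exploratory biomarker models. The primary ORR decision rules are untouched. The wording should be corrected before analysis.

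**What to change.** In section 10.3:

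- Define PFS as time from treatment initiation, stating whether that is induction day 1 or Cycle 1 Day 1, to the first of documented RECIST 1.1 progression or death from any cause. Date progression at the first scan showing it, not at the confirming scan.
- Censor patients who are alive and progression-free at their last tumour assessment.
- Define duration of response from first documented CR or PR to progression or death, in CR/PR patients only. Alternatively, keep the present quantity, call it duration of clinical benefit, state the start date when stable disease comes first, and use one clinical-benefit definition for irRECIST (section 6.2 or 10.3).

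The cost is a few sentences, with no new visits or data, because survival and progression are already followed (sections 4.7 and 4.8). Reported PFS may come out lower than if such deaths were dropped or censored. A responder-only duration will rest on few patients: 0.20 × 24 = 4.8, about 5 of 24 at an ORR of 20%.
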